### 9.2.2 Serious adverse events (SAEs)

A serious adverse event is any untoward medical occurrence or effect that

- results in death;
- is life threatening (at the time of the event);
- requires hospitalisation or prolongation of existing inpatients' hospitalisation;
- results in persistent or significant disability or incapacity;
- is a congenital anomaly or birth defect; or
- any other important medical event that did not result in any of the outcomes listed above due to medical or surgical intervention but could have been based upon appropriate judgement by the investigator.

An elective hospital admission will not be considered as a serious adverse event.

The illness in this study population, consisting of cancer and lung diseases, cardiology-, cardiothoracic surgery- and orthopaedic conditions often progresses to a life-threatening stage due to the advanced nature of their disease. Similarly, prolonged hospitalizations are frequent among cancer patients due to the need for ongoing treatment, as well as among lung and cardiology/cardiothoracic surgery patients who may experience complications related to their disease and treatment conditions with no relation to the study interventions. Additionally, congenital anomalies or birth defects are not relevant to this study population, these conditions are not typically seen.

Therefore, the investigator will report all SAEs to the sponsor without undue delay after obtaining knowledge of the events, except for the following SAEs:

- is life threatening (at the time of the event);
- requires hospitalisation or prolongation of existing inpatients' hospitalisation;
- is a congenital anomaly or birth defect

The sponsor will report the SAEs through the web portal *Research Portal* to the review committee that approved the protocol, within 7 days of first knowledge for SAEs that result in death or are life threatening followed by a period of maximum 8 days to complete the initial preliminary report. All other SAEs will be reported within a period of maximum 15 days after the sponsor has first knowledge of the serious adverse events.

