# **9. SAFETY REPORTING**

## **9.1 Temporary halt for reasons of research participant safety**

In accordance to section 10, subsection 4, of the WMO, the sponsor will suspend the study if there is sufficient ground that continuation of the study will jeopardise participant health or safety. The sponsor will notify the review committee without undue delay of a temporary halt including the reason for such an action. The study will be suspended pending a further positive decision by the review committee. The investigator will take care that all participants are kept informed.

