## **9.2 AEs, SAEs**

### **9.2.1 Adverse events (AEs)**

Adverse events are defined as any undesirable experience occurring to a participant during the study, whether or not considered related to oral nutritional supplements intervention or study procedures. All adverse events reported spontaneously by the participant or observed by the investigator or his staff will be recorded.

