### **9.3 Follow-up of adverse events**

All AEs will be followed until they have abated, or until a stable situation has been reached. Depending on the event, follow up may require additional tests or medical procedures as indicated, and/or referral to the general physician or a medical specialist. SAEs need to be reported till end of study within the Netherlands, as defined in the protocol.

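### Section 9.2.2 exempts life-threatening and hospitalisation SAEs from prompt reporting to the sponsor whatever their cause, which is wider than its own rationale

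*Protocol*

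**What the plan says.** Section 9.2.2 of the protocol lists six criteria that make an adverse event serious, and notes that elective admissions do not count. It then explains why some categories are expected in this population. Life-threatening states are put down to the advance of the underlying disease. On hospital stays it says that "prolonged hospitalizations are frequent among cancer patients due to the need for ongoing treatment", and that lung and cardiology/cardiothoracic patients may have "complications related to their disease and treatment conditions with no relation to the study interventions". Congenital anomalies are described as not relevant.

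From this it draws the rule: "Therefore, the investigator will report all SAEs to the sponsor without undue delay after obtaining knowledge of the events, except for the following SAEs". The list that follows names life-threatening events, hospitalisation or its prolongation, and congenital anomaly, with no condition on cause or relatedness.

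The next paragraph has the sponsor report onward to the review committee "within 7 days of first knowledge for SAEs that result in death or are life threatening", and report other SAEs within 15 days. Section 9.1 says that "the sponsor will suspend the study if there is sufficient ground that continuation of the study will jeopardise participant health or safety".

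**The concern.** The rule goes further than the argument for it. The argument concerns events that arise from the disease or its treatment; the exemption takes in every event in the category, including one the investigator suspects the supplement caused.

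The sponsor has to judge whether the study should be suspended. If section 9.2.2 is followed to the letter, the sponsor need not be told promptly of a survived life-threatening reaction or unplanned admission that may be product-related. The trial has no data safety monitoring board (section 9.4) and no monitoring (section 12.2), so neither would pick up such an event. Section 6.3 states that this plant-based product has not been studied before, so an unforeseen reaction cannot be dismissed on earlier trial evidence with it.

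**Working it through.** No stated figure is at issue, so the check is a comparison of the text, followed by a search for another route to the sponsor.

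**Step 1. Exemption against rationale (section 9.2.2).**

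| SAE criterion | Reason given for exempting it | Exempt? |
|---|---|---|
| Death | none | no |
| Life-threatening | progression of the underlying disease | yes, any cause |
| Hospitalisation or prolongation | prolonged stays for treatment in cancer; unrelated complications in lung and cardiology/cardiothoracic patients | yes, any cause |
| Persistent or significant disability | none | no |
| Congenital anomaly | not relevant to this population | yes |
| Other important medical event | none | no |

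The count: 6 criteria, 3 exempt, 6 − 3 = 3 still promptly reportable. Setting congenital anomaly aside as irrelevant leaves 6 − 1 = 5 relevant criteria, of which 3 − 1 = 2 are exempt.

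The hospitalisation exemption exceeds its rationale in three ways. It covers new unplanned admissions as well as prolonged stays. It covers orthopaedic patients, whom the hospitalisation sentence does not name. It covers events related to the supplement. The life-threatening exemption exceeds its rationale in the last way.

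**Step 2. Does the residual criterion recapture these events?** No. It is worded as "any other important medical event that did not result in any of the outcomes listed above due to medical or surgical intervention", so it applies to events that stopped short of a listed outcome. The result is an inversion. A reaction that treatment kept from becoming life-threatening must be reported promptly, while the same reaction, if it did become life-threatening and the patient recovered without disability, is exempt.

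**Step 3. Does the sponsor's 7-day duty close the gap?** No. Its clock starts when the sponsor first knows. It does not contradict the exemption, but for survived life-threatening events nothing obliges anyone to give the sponsor that knowledge.

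**Step 4. Is there another required prompt route?**

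- Section 9.2.1: adverse events are recorded, with no transmission to the sponsor and no time limit.
- Section 9.3: events are followed up, and "SAEs need to be reported till end of study within the Netherlands, as defined in the protocol". This sets a period and refers back to the same rule.
- Sections 3 and 8.3: contacts fall at 0, 1, 2 and 3 months, so a researcher may hear of an event within about one month. The listed content of the month 1 and month 2 check-ins includes no SAE report to the sponsor. Length of stay and readmissions are collected retrospectively, and complications are taken from the patient record.
- Section 8.4: withdrawal for urgent medical reasons carries no notice to the sponsor.
- Section 12.1: access to the data is not notification.
- Section 12.4: the yearly summary includes SAEs but goes to the funder.
- Sections 8.7 and 12.5: these govern notices about termination, halt and end of study, not notices of individual events to the sponsor.

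None of these requires prompt notice to the sponsor of an exempt event.

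**The case against.** Exempting events that the disease makes frequent is ordinary practice, and the protocol gives its reason openly. Both products are on the market and used in hospitals. Section 13.1 cites a study of a different plant-based supplement that found it well tolerated and safe, and section 13.2 rates the overall risk as negligible. People with known lactose intolerance or soy allergy or intolerance are excluded. Deaths, disabling events and other important medical events remain reportable, and all observed or volunteered adverse events are recorded. The sponsor is also one of the two participating centres (section 8.7), so it may well hear of events there without a formal rule. Counting criteria says nothing about how many events would be missed.

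Most of this stands, and it limits the weight of the point. The gap is confined to survived, non-elective events without lasting disability, it matters most at the centre that is not the sponsor, and the likely number of product-related cases is low. None of it supplies the missing duty. Informal knowledge at one centre is not a rule and leaves the other uncovered. Exclusion criteria catch only conditions already known. The usual practice being defended is an exemption for disease-related events, and the text does not contain that limit.

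**Conclusion.** The point holds and should be fixed. Section 9.2.2 releases two of the five relevant SAE criteria from prompt investigator-to-sponsor reporting regardless of cause, although its own reasoning supports this only for events unrelated to the study products. For a survived, possibly product-related event of either kind, no required prompt route to the sponsor exists anywhere in the protocol.

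The practical hazard is small and the feasibility endpoint is not affected. The documents give no event rates, so the number of events concerned among the 60 participants, each followed for 3 months, cannot be stated. The conclusion assumes that an event meeting both an exempt and a non-exempt criterion, such as a life-threatening event that leaves lasting disability, stays reportable.

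**What to change.** Reconcile the exemption list with its rationale, so that the 7-day duty also has an input for survived events. Limit the exemption to life-threatening and hospitalisation SAEs that the investigator records as due to the underlying disease or its treatment and unrelated to the supplement or study procedures; all others in those categories then go to the sponsor promptly. The protocol already draws this distinction in section 9.2.1, where adverse events are defined "whether or not considered related to oral nutritional supplements intervention or study procedures". Add a relatedness entry to the adverse event form if it lacks one; the form is not shown.

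A separate small correction can be made at the same time. Section 9.2.2 sends the sponsor's reports to the committee that approved the protocol, while sections 11.5 and 12.2 describe the study as exempt from review and outside the WMO. The protocol should say who receives these reports.

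The cost is one or two sentences in section 9.2.2, and possibly one form field. It needs no extra visits, measurements or participants. The number of additional reports cannot be derived from the protocol.

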### **9.3 Follow-up of adverse events**

All AEs will be followed until they have abated, or until a stable situation has been reached. Depending on the event, follow up may require additional tests or medical procedures as indicated, and/or referral to the general physician or a medical specialist. SAEs need to be reported till end of study within the Netherlands, as defined in the protocol.

### **9.4 Data Safety Monitoring Board (DSMB) / Safety Committee**

Not applicable

## **10. STATISTICAL ANALYSIS**

The Statistical Package for the Social Sciences for Windows (version 29.0; IBM, SPSS Inc., Chicago, IL, USA) will be used for statistical analysis. Descriptive statistics will be used to explore the data and will be presented in tables and figures. Normally distributed data will be expressed as mean and standard deviation or as median, interquartile range, and minimum and maximum. Categorical data will be summarized by frequency or percentage.

### **10.1 Primary study parameter(s)**

The primary analysis will explore the feasibility of a multicenter RNIT comparing plant-based and animal-based ONS in patients at risk of malnutrition with respect to the patient recruitment, drop-out rate, adherence, and the feasibility of study measurements.

### **10.2 Secondary study parameter(s)**

Secondary analysis will provide the mean difference in protein intake i.e., total protein intake in g/kg FFM/d (based on dietary history) divided by 1.5-1.9 g/kg FFM/d, times 100%. In addition, the mean difference in energy intake i.e., total energy intake in kcal/d (based on dietary history) divided by WHO formula + surcharge up to 50%, times 100%. ANCOVA analysis will be used to estimate the effect of the group as independent factor on 'mean difference in intake vs recommendation' at T3 as dependent variable and T0 measurement as covariate. This is only meant as exploratory analyses and to be used for sample size calculations for the subsequent full-scale RCT.

The aim of the semi-structured interviews is to understand the experiences and perspectives of the patients using ONS regarding satisfaction (taste, smell, satiety), as well as their wishes and needs. Additionally, we are interested in their views of

sustainable nutrition. Therefore, these interviews will be approached from a phenomenological perspective. Qualitative analysis: all interviews will be audiotaped, and the records will be transcribed verbatim. Data will be analyzed using thematic analysis, starting with initial open coding to identify relevant data by minimal two independently working researchers. Codes will then be grouped into categories, the axial codes, and overarching themes will be identified. For this analysis, the software Atlas.ti will be used.

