**3. STUDY DESIGN**

This study is a pilot randomized feasibility study in patients with cancer and lung diseases, cardiology patients, patients with cardiothoracic surgery, and orthopaedic patients at risk for inadequate nutritional intake to evaluate feasibility and patient satisfaction necessary to determine a suitable patient population and calculate the sample size for a larger RNIT (i.e. study 2). In study 2, a large RNIT will be conducted to establish the long-term efficacy of plant-based vs animal-based ONS. During this pilot study, patients who are advised ONS according to usual care and signed informed consent (IC) will be randomized to receive either plant-based ONS or animal-based ONS. Several measurements will be performed at 0 and 3 months. A total of 60 patients will be included. The main aim is to establish the feasibility in terms of recruitment, drop-out rate, adherence, and study measurements of the different subpopulations, reflecting feasibility for performing study 2. Furthermore, we will collect data on protein and energy intake, which will be used for the sample size calculation of study 2. Apart from the quantitative measurements, study 1 will also be setup as a qualitative study to determine patients' satisfaction, wishes and needs towards the ONS. Data on patients' satisfaction will only be used as observational data, no comparison between the two types of products will be made.

Measurements will be performed during hospital admission, or before/after an already scheduled appointment at the hospital outpatient clinic (baseline T0), and three months after baseline (T3). Within these 3 months, patients will be contacted by the researcher 1 month after the start (T1) and 2 months after the start (T2) for a 'check-in' conversation. For this conversation the researcher will either make a phone call or have brief conversation at the

hospital if the patient is already there for another appointment. The researcher will ask about any changes in body weight, discuss changes in the nutritional advice provided by the dietitian, ensure the patient is still correctly filling out the logbook, and address any questions or concerns related to the study. The study will be conducted at Radboud university medical center (Radboudumc) in Nijmegen, the Netherlands, and Maastricht University Medical Center (Maastricht UMC+) in Maastricht, the Netherlands.

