### **8.2 Randomisation, blinding and treatment allocation**

Patients will be randomized to either the plant-based ONS or animal-based ONS. Randomisation will be done by Castor EDC database. This system will generate the randomisation performed by stratification for 3 different patient populations: (1) oncology, (2) pulmonary diseases (3) other (including cardiology, cardiothoracic surgery, orthopaedic patients) and for the study location (Radboudumc and Maastricht UMC+). In this way, it will be done independently. Patients can not be blinded in this study since it is

not feasible to cover every bottle the patients drink in those 3 months (i.e. patients will receive already existing products with standard packaging and labelling). Nevertheless, the analyses will be carried out in a blinded manner.

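### The exploratory intake ANCOVA that feeds study 2's sample size omits the two factors by which randomisation is stratified (minor)

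*Protocol*

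**What the plan says.** Section 8.2 describes "randomisation performed by stratification for 3 different patient populations": oncology, pulmonary diseases, and a third group combining cardiology, cardiothoracic surgery and orthopaedics. It also stratifies by the two study locations. That gives 3 x 2 = 6 strata.

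Section 10.2 writes out the model for intake as a percentage of recommendation: "ANCOVA analysis will be used to estimate the effect of the group as independent factor", with the outcome "at T3 as dependent variable and T0 measurement as covariate". No other term is named there, and no other section adds one.

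On purpose, section 10.2 states: "This is only meant as exploratory analyses and to be used for sample size calculations for the subsequent full-scale RCT". Section 3 agrees: "we will collect data on protein and energy intake, which will be used for the sample size calculation of study 2". It also says that the pilot's findings are "necessary to determine a suitable patient population and calculate the sample size for a larger RNIT".

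Section 4.4 sets a convenience sample of 60, 30 per group. Section 8.5 rules out replacing participants who withdraw.

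**The concern.** When randomisation is balanced within strata, the group difference is estimated free of any between-stratum differences. A model that ignores the strata nevertheless leaves those differences in its residual variance. Its standard error then describes a less precise experiment than the one performed, and its residual SD mixes within-stratum scatter with differences between populations and sites.

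For an exploratory comparison this would hardly matter alone. Here the residual SD is the quantity to be carried forward. A study 2 that again stratifies and adjusts would be planned on a larger SD than its own analysis would meet, so it would on average be larger than needed. The protocol mixes oncology, lung, cardiac, cardiothoracic and orthopaedic patients, so a population effect on intake is plausible, though the protocol gives no information on its size.

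**Working it through.** **Inputs from the protocol.** N = 60, 30 per group (section 4.4); population with 3 levels and site with 2 (section 8.2); model terms group and T0 (section 10.2). The sample of 60 rests on no SD, margin, alpha or power, so there is no stated calculation to reproduce.

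**Assumptions.** R2 is the share of the variance left after group and T0 that population and site explain. The protocol gives no value, so a range of 0 to 0.20 is shown. A 20% drop-out (48 patients analysed) is also assumed where used.

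**Average effect on the SD and on n.** The residual SD without the strata, relative to the SD with them, is 1/sqrt(1 - R2). For a fixed margin n is proportional to SD squared, so the n ratio is 1/(1 - R2).

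| Assumed R2 | SD ratio | n ratio |
|---|---|---|
| 0 | 1.000 | 1.00 |
| 0.05 | 1/sqrt(0.95) = 1.026 | 1/0.95 = 1.05 |
| 0.10 | 1/sqrt(0.90) = 1.054 | 1/0.90 = 1.11 |
| 0.20 | 1/sqrt(0.80) = 1.118 | 1/0.80 = 1.25 |

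As an illustration, take a non-inferiority margin of 0.4 SD, one-sided alpha 0.025 and 80% power (all assumed). Study 2 then needs 99 per arm with the unadjusted SD, against 89 at R2 = 0.10 and 79 at R2 = 0.20.

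**Degrees of freedom.** Without strata, 60 - 3 = 57. With population (2 df) and site (1 df), 60 - 6 = 54. With 48 patients these become 45 and 42.

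**Sampling error of the SD.** The 95% limits are sqrt(df/chi-square quantile) times the estimate: 0.845 to 1.224 at 57 df and 0.842 to 1.232 at 54 df. The extra terms cost almost no precision. The 12% shift at R2 = 0.20 lies inside these limits.

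**Check by simulation.** Settings: 20,000 pilots each, six strata of 10, 1:1 within stratum, T0-T3 correlation 0.5, additive stratum effects, no group effect, N = 60.

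| Assumed R2 | Coverage of 95% interval, strata omitted | Pilots in which adding strata raises the residual variance |
|---|---|---|
| 0 | 95.0% | 60% |
| 0.05 | 95.5% | 26% |
| 0.10 | 96.2% | 9% |
| 0.20 | 97.0% | 1% |

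With the strata included, coverage is 94.9% to 95.1% throughout. The mean SD ratios (1.000, 1.027, 1.056, 1.122) match the formula. With 48 patients the last column becomes 60%, 31%, 15% and 2%. A second simulation, with blocks of 4 and strata of unequal size (8,000 pilots), gives two-sided rejection rates without strata of 4.8%, 3.6% and 3.2% at R2 = 0, 0.10 and 0.20, against 4.8%, 4.7% and 5.2% with them. Both show that the error is conservative, and that one pilot can move either way when R2 is small.

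**The case against.** The strongest defence is that little rests on this model. It is labelled exploratory, the primary endpoint is feasibility, and no margin or progression decision depends on it. Every R2 above is assumed. Adjustment for T0, and expressing intake relative to requirement, may already absorb much of any difference between populations. At R2 of 0.05 to 0.10 the SD shifts by 3% to 5%, which is small against its sampling error. Population and site are recorded for randomisation, so the adjusted model can be fitted later without new data. All of this stands, and it keeps the point minor.

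It could also be said that covariate lists belong in a statistical analysis plan. That carries less weight here, because the protocol does not leave the model open: it names the factor, the outcome and the covariate.

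A further objection limits the remedy. Study 2's design is not fixed. If it does not adjust for strata, the unadjusted SD is the relevant one. If it keeps one population, additive factors still give one SD pooled over all populations, which suits that population only if variances are similar. A reader might infer that adding the factors supplies the single-population SD; it does not.

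**Conclusion.** The point holds as a minor one. The model written in section 10.2 does not reflect the stratification in section 8.2. If the strata are prognostic beyond T0, its standard error and residual SD are too large on average. The size depends wholly on the assumed R2, and there is no expected effect if the strata are not prognostic. The n ratios also assume a study 2 that stratifies and adjusts as the pilot would, with a margin fixed in the units of the outcome.

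Two stronger readings are not supported:

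- A reader might infer that the group comparison is biased or the pilot compromised. Neither follows: the omission costs only precision in a secondary, exploratory analysis.
- A reader might infer from the range in the outcome's denominator ("total protein intake in g/kg FFM/d (based on dietary history) divided by 1.5-1.9 g/kg FFM/d, times 100") that the SD is undefined by a large factor. Section 8.3 says that an individual requirement is set under cited guidelines, which are not at hand. Nothing in the protocol proposes applying one end of the range to everyone. How each patient's value is chosen is unstated detail, not an error in the plan.

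**What to change.** In section 10.2, add patient population (three levels) and site (two levels) as factors to the ANCOVA, alongside group and the T0 value. Report the residual SD, with confidence limits, with and without these factors. State that the adjusted SD will be used for study 2 if study 2 is stratified and adjusted in the same way. If study 2 keeps a single population, also report that population's SD descriptively, and note that the pooled SD applies to it only if variances are similar.

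The change is wording only, needs no new data or visits, and uses the 3 model degrees of freedom counted above.
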